5.6. Per-Protocol Set

The Per-Protocol Set (PPS) and Per-Protocol Set for Incontinence (PPS-I) exclude patients from the FAS due to important deviations from the protocol that may substantially affect the results of the primary efficacy endpoints (i.e., Major PDs associated with efficacy). A supportive analysis using the PPS and PPS-I will be performed for the co-primary and key

secondary efficacy endpoints. The final determination on protocol deviations, and thereby the composition of the Per-Protocol Sets, will be made prior to the unblinding of the database and will be documented per the Protocol Deviation Plan during the BDRM.

Patients will be included in the treatment group to which they are randomized, regardless of which treatment actually received, for the analyses of efficacy data using the PPS and PPS-I.

5.7. Pharmacokinetic Set

The PK set will include all patients in the Safety Set who undergo plasma PK sampling and have evaluable PK assay results.

5.8. Protocol Deviations

Protocol deviations are collected and agreed at the Protocol Deviation review meetings occurring prior to database lock (DBL); to evaluate protocol deviations considered to have a major impact on patient safety, efficacy or the validity of the study data. The protocol deviations are classified into 5 major categories and 1 minor category. The major categories are as follows:

- Major (Efficacy)
- Major (Efficacy Duplicate Patient)
- Major (Efficacy and Safety)
- Major (Safety)
- Major (Other)

Patients with major efficacy protocol deviations, which includes the 3 major categories above associated with efficacy, will be excluded from the PPS and PPS-I under the assumption that the deviation may have an impact on the efficacy analysis. Efficacy protocol deviation categories may include, but are not limited to the following:

- Inclusion/Exclusion Criteria Not Met
- Concomitant Medication (Prohibited Meds)
- Missed Study Visit
- Visit Out of Window
- Other (e.g. IP Compliance)
- Procedure Not Per Protocol

Other Major protocol deviation categories may include, but are not limited to the following:

- Informed Consent Issues
- IP Dispensation/Storage
- Lab Sample Issues (Missing/Not Analyzed etc.)
- AECI Not Reported

All major protocol deviations related to efficacy will be discussed during the BDRM, and decisions relating to exclusion for the PPS(-I) will be documented in the BDRM Report, finalized prior to unblinding.

6. GENERAL ASPECTS FOR STATISTICAL ANALYSIS

6.1. General Methods

All patients entered into the database will be included in patient data listings. Summary tables will be provided for all randomized patients. Unless otherwise specified; all demographic and baseline data will be presented by treatment arm and overall. Efficacy and safety data will be presented by treatment arm.

Although the formal analysis will compare vibegron with placebo, the comparisons between tolterodine and placebo will be reported with nominal p-values. No formal comparisons of vibegron vs. tolterodine are planned; all between-treatment analyses between these two groups will be considered descriptive.

Quantitative (continuous) data - absolute values and changes from baseline, where appropriate - will be summarized with the population sample size (N), number of patients with available data (n), mean, standard deviation (SD), median, minimum, Q1, Q3 and maximum.

Qualitative (categorical) data will be summarized using the population sample size (N), number of patients with available data (n), frequency and percentages of patients. Unless stated otherwise, the calculation of percentages will be based on the total number of patients with non-missing data (n) in the set of interest.

The primary population for efficacy analysis will be the FAS for micturition endpoints while the FAS-I will be used for the following incontinence endpoints: UUI, total incontinence episodes, percent of dry diary days. Supportive efficacy analyses based on the PPS and PPS-I will be conducted for the primary and key secondary endpoints. The SAF will be used to conduct analyses of the safety endpoints. All PK data will be based on the PK Analysis set (PKS).

6.2. Testing Strategy and Multiplicity

A stepwise gate-keeping procedure will be used to control the overall Type-I error rate at $\alpha=0.05$ level (two-sided) over the co-primary and key secondary hypotheses. If significance at the 0.05 level of both co-primary efficacy endpoints is achieved, then the key secondary efficacy endpoints will be tested sequentially in the predefined order given in [Section 4.2](#). Once a key secondary efficacy endpoint is found to be insignificant (i.e., p-value ≥ 0.05), the testing procedure will stop. For all subsequent key secondary efficacy endpoints, nominal p-values will be provided but will not be considered a formal test of hypotheses.

All other additional and exploratory efficacy endpoints will be considered supportive and no multiplicity adjustments will be performed for these other efficacy endpoints. Nominal p-values will be computed for other efficacy endpoints as a measure of the strength of association between the endpoint and the treatment effect rather than formal tests of hypotheses. Unless otherwise stated, all statistical tests will be conducted at the (two-sided) $\alpha=0.05$ level of significance.

6.3. Key Definitions

The patient voiding diary asked patients to record what time they woke up for the day, what time they went to bed, and asked the patients to record every time they had a urination event. For each event, patients recorded the time, if they had a need to urinate immediately, if they urinated in the toilet, if they had accidental urine leakage, and if they had leakage what the reason was for the leakage (urge, stress, or other). The following are key definitions based on the diary data:

Diary Parameters

Micturition

A micturition/void is defined as “Urinated in Toilet” as indicated on the voiding diary.

Urgency Episodes

An urgency episode is defined as the “Need to Urinate Immediately” as indicated on the voiding diary.

Urge Urinary Incontinence (UUI) Episodes

A UUI episode is defined as having "urge" as the main reason for the leakage as indicated on the voiding diary, regardless of whether more than one reason for leakage in addition to “urge” is checked.

Total Incontinence

Total incontinence is defined as having any reason for “Accidental Urine Leakage” and/or “Accidental Urine Leakage” checked, as indicated on the voiding diary. It is assumed that if the patient recorded a reason for leakage then the accidental urine leakage occurred.

Nighttime Voids Associated with Urgency (NVU)

An NVU is defined as the “Need to Urinate Immediately” occurring after going to bed, but prior to getting up the next day.

Nighttime Voids

A nighttime void is defined as “Urinated in Toilet” as indicated on the voiding diary, after going to bed but prior to getting up the next day.

Nighttime UUI

A nighttime UUI episode is defined as having "urge" as the main reason for the leakage as indicated on the voiding diary, regardless of whether more than one reason for leakage is checked, and occurring after going to bed, but prior to getting up the next day.

OAB Categorization

There will be two different definitions of OAB Categorization used for the study: OAB Type and OAB-d Type. OAB Type will be based on the randomization strata and OAB-d Type will be derived based on the baseline diary data, defined below. Details on the derivation of baseline patient voiding diary endpoints are presented further below in this section (Definition of Baseline for Patient Voiding Diary Endpoints).

OAB-d Type (Wet, Dry, Missing) will be categorized based on Baseline diary data, as follows:

OAB Wet: Patients are considered OAB Wet according to the following criteria:

- An average of ≥ 8.0 micturitions per Diary Day; and,
- An average of ≥ 1.0 UUI episodes per Diary Day; and,
- If stress urinary incontinence (SUI) is present, the total number of UUI episodes must be greater than the total number of SUI episodes.

OAB Dry: Patients are considered OAB Dry according to the following criteria:

- An average of ≥ 8.0 micturitions per Diary Day; and,
- An average of ≥ 3.0 urgency episodes per Diary Day; and,
- An average of < 1.0 UUI episodes per Diary Day

OAB-d Type Missing: Patients are considered non-categorized for OAB if neither of the above criteria is achieved.

Where OAB Wet is discussed in this document, it pertains to patients randomized under the strata of OAB Wet; where all OAB Patients are discussed, this relates to all patients randomized as either OAB Wet or OAB Dry. Under the randomization strata, all patients are categorized as OAB Wet or Dry; missing is not present. Unless otherwise stated, for the purposes of the analyses, OAB Type (i.e. as randomized) will be used.

Diary Day

A “Diary Day” is defined as the time between when the patient gets up for the day each morning and the time the patient gets up for the day the next morning as recorded in the patient voiding diary.

Complete Diary Day

A “Complete Diary Day” is defined as a Diary Day that includes input of micturition data by patients on the voiding diary. Unless a patient indicated “No” to the questions of “Did you record each time you urinated or leaked during this Diary Day” the Diary Day is considered complete.

For post-baseline diaries at Weeks 4 and 8, only complete diary days within 10 days prior to the study visit will be included. For the Week 12/Early Termination diary, only complete diary days within 14 days prior to the study visit will be included. For the Week 2 diary, complete diary days within 10 days prior to the target Week 2 day will be used. For diaries at all visits, if a patient has fewer than 4 complete diary days, that will be identified as a significant protocol deviation and that diary data will be excluded from all analysis.

Definition of Baseline for Patient Voiding Diary Endpoints

Baseline will be the data collected during the Run-in Period. If greater than 10 complete diary days are available in the Run-in diary, only the complete diary days within the 10 days prior to the Baseline visit will be used; if 4 or more and less than 10 complete diary days are available, all complete diary days in the Run-in diary will be used to calculate Baseline. If less than 4 complete diary days are available, the Baseline will be regarded as missing. For a patient to have an evaluable change from baseline, the patient must have both a baseline diary and a post-baseline diary from any post-baseline timepoint, after analysis window has been applied (i.e., Week 2, Week 4, Week 8, or Week 12).

Definition of Baseline for Endpoints not Derived from the Patient Voiding Diary

Baseline value for all secondary efficacy, exploratory and safety endpoints will be defined as the last non-missing assessment before starting double-blind treatment.

Screening/Washout Period

The Screening/Washout Period covers Day -49 (Screening Visit) to Day -15 (the day before the start of the Run-in Period), which includes a 28-day washout period followed by 7-days of Diary completion. Patients not requiring the 28-day washout period can begin the 7-day Diary the day after the Screening Visit.

Run-in Period

The Run-in Period covers the duration between screening (Day -14) and the day before baseline (Day 1). There is no day 0 included in the study.

Treatment Period

The Treatment Period covers the duration that a patient is in the study from Baseline (Day 1) and Week 12.

Safety Follow-up Period

The Safety Follow-up Period continues for 28 days after the last dose of study treatment (Day 85) through Day 113 (Follow-up Visit).

Definition of Study Completion

A patient will be defined as “completed” if she/he completes the Week 12 study visit.

End of Study Definition

End of study is defined as the date when the patient has completed one of the following: completed the follow-up visit after the Week 12 visit, enrolled into the extension trial 3004, permanently discontinued from the study, or lost to follow-up. When lost to follow-up, the latest date of assessment/event in the database will be used as the last known date of the patient in study.

Day of Study Event (Post-Randomization)

Day of study event = Event Date – Date of Randomization (Day 1) + 1.

Day of Study Event (Pre-Randomization)

Day of study event = Event Date – Date of Randomization (Day 1).

Change from Baseline

Absolute CFB = Post-baseline value – Value at baseline

Percent Change from Baseline

Percent CFB = $100 * (\text{Post-baseline value} - \text{Value at baseline}) / \text{Value at baseline}$

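### SAP section 6.3 defines nighttime voids associated with urgency (NVU) by the urgency item alone, so nighttime urgency events without a toilet void count as NVUs

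*SAP*

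**What the plan says.** SAP section 6.3 (Key Definitions) builds its diary measures from separate items recorded for each event. Patients noted "if they had a need to urinate immediately, if they urinated in the toilet, if they had accidental urine leakage", and the reason for any leakage. From these items the section defines:

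- Void: "A micturition/void is defined as “Urinated in Toilet” as indicated on the voiding diary".
- Nighttime void: "A nighttime void is defined as “Urinated in Toilet” as indicated on the voiding diary", limited to the time between going to bed and getting up.
- Urgency episode: "An urgency episode is defined as the “Need to Urinate Immediately” as indicated on the voiding diary".
- NVU: "An NVU is defined as the “Need to Urinate Immediately” occurring after going to bed", with the window closing when the patient rises. The label over this definition reads "Nighttime Voids Associated with Urgency (NVU").

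The glossary in section 1 also describes the NVU as voids. Nighttime UUI has its own definition in section 6.3, based on urge as the main reason for leakage in the same nighttime window.

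**The concern.** By its name, an NVU is a kind of nighttime void: one that comes with urgency. By its definition, it need not be a void at all. The toilet item that makes an event a void elsewhere in section 6.3 is absent, and no visible text of the SAP adds it.

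Two things follow. First, a nighttime urge leak with the urgency item checked and no toilet void enters both nighttime UUI and NVU, so fewer nighttime leaks could be reported as fewer nighttime voids with urgency. Second, a programmer who follows the label and one who follows the sentence would obtain different counts. Section 6.2 provides nominal p-values for additional and exploratory efficacy endpoints, so a measure under the wrong name could carry one if it is analysed there.

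**Working it through.** No sample size, power, alpha or stated figure depends on this point, so there is no plan figure to reproduce. The check applies the section 6.3 definitions to the possible diary entries.

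**Step 1. Can the two readings differ?** Urgency, toilet void and leakage are separate items for each event. The completeness question in section 6.3 (Complete Diary Day) asks whether the patient recorded every urination or leak, so leaks are meant to be recorded as well as voids. A nighttime entry with urgency and leakage but no toilet void is therefore possible.

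**Step 2. Classify a nighttime event with urgency checked.**

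| Toilet item | Leakage item | NVU as written | NVU if a void is required | Nighttime void |
|---|---|---|---|---|
| yes | yes or no | 1 | 1 | 1 |
| no | yes | 1 | 0 | 0 |
| no | no (if such an entry is made) | 1 | 0 | 0 |

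The readings agree whenever the toilet item is checked and differ whenever it is not.

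**Step 3. A hypothetical night** with one urgency void, one urgency event with leakage only, and one void without urgency:

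- NVU as written: 1 + 1 + 0 = 2.
- NVU with a void required: 1 + 0 + 0 = 1.
- Nighttime voids: 1 + 0 + 1 = 2.

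Only one event that night was a void with urgency, yet the written rule returns 2.

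**Step 4. The limiting case.** If the only nighttime event is an urgency leak with no toilet void, NVU as written is 1 and nighttime voids are 0. A quantity named as a subset of nighttime voids then exceeds them.

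**Step 5. Where it reaches.** NVU does not appear among the co-primary endpoints (section 4.1), the key secondary endpoints (4.2) or the additional secondary endpoints (4.3), so it has no part in the gatekeeping of section 6.2. The exploratory endpoint text (sections 4.6, 8.4 and 8.5) is not visible in the public copy. Where NVU is analysed, and whether a void condition is added there, cannot be checked.

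**The case against.** The best defence is that the written rule is explicit and reproducible. It uses the same diary item as the key secondary urgency endpoint, limited to the night, and counting all nighttime urgency is a defensible choice. On that view only the label is wrong. Nighttime voids and nighttime UUI are defined separately, so a fall in NVU driven by leaks could be checked against them. Section 6.3 also describes diary entries as urination events, so urgency may usually accompany a void.

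Much of this stands. The rule can be programmed as it is, and entries without a void may be uncommon. But the label and the rule still describe different quantities, and the completeness question shows that leaks are expected in the diary.

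The defence also exposes a real cost of requiring a void. Suppose a patient's nighttime urge leak without a toilet void becomes, on treatment, a dry urgency void. As written, NVU stays at 1. With the void condition it rises from 0 to 1 while nighttime UUI falls from 1 to 0, so an improvement would look like a worsening on NVU alone.

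A reader might go further in three ways that the SAP does not support:

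- *That leak-only events inflate the void counts.* They do not. Micturitions and nighttime voids both require the toilet item, so these events enter the NVU count only.
- *That a confirmatory result is at risk.* NVU is in none of the visible endpoint lists, and additional and exploratory p-values are nominal under section 6.2.
- *That the over-count can be sized from the OAB Wet population.* The 75% OAB Wet share in section 3.8 is a planning assumption, and the threshold of 1.0 UUI episodes in section 6.3 is per Diary Day, not per night. Neither gives the share of nighttime urgency events that lack a toilet void.

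**Conclusion.** The mismatch is certain from the text of section 6.3: the NVU as written is the count of nighttime urgency episodes and need not be a subset of nighttime voids. Its practical weight is small. No co-primary, key secondary or additional secondary endpoint changes, and no void count changes. The size of the over-count cannot be estimated, because the SAP reports no frequency of nighttime urgency events without a toilet void.

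The conclusion rests on two conditions: that the diary accepts an entry with urgency and no toilet void, which the separate items and the completeness question indicate, and that the exploratory text not shown adds no void condition. It is a minor correction, worth making because it is nearly free.

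**What to change.** Before unblinding, amend the NVU definition in section 6.3 so that an event counts only if the toilet item and the urgency item are both checked on that same event, between going to bed and getting up. If all nighttime urgency is of interest, report it as a separate measure named nighttime urgency episodes, using the present rule.

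The cost is one sentence in the SAP and one condition in the derivation program. To handle the downside described above, present NVU beside nighttime UUI, which the SAP already defines, so that leaks converted to dry urgency voids can be recognised.

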3.11. Study Procedures and Flowchart

This study consists of a Screening Period (1 to 5 weeks), a single-blind Run-in Period (2 weeks), a randomized double-blind Treatment Period (12 weeks) and a Safety Follow-up Period (4 weeks). The schedule of activities is given in [Table 3.11.1](#).

Table 3.11.1: Schedule of Activities

Study Period:	Screening/ Washout	Run-in	Treatment					Safety Follow-up/ Unscheduled	
Visit Number:	Visit #1	Visit #2	Visit #3	Diary Only	Visit #4	Visit #5	Visit #6	UNS #	Visit #7
Visit Name:	Screening ¹	Run-in	Baseline	Week 2	Week 4	Week 8	Week 12 or Early WD	Unsch- eduled ²⁵	Follow- up ²⁶
Study Day:	-49 to -15	-14	1	15	29	57	85 or Early WD		113 or Early WD + 28
Permitted Visit Window:		± 3 Days			± 3 Days	± 3 Days	± 3 Days		± 3 Days
Informed Consent	X								
Inclusion/Exclusion Criteria Eligibility Review	X	X	X						
Medical and Medication History	X	X	X						
Electronic Diary (eDiary) ² :									
eDiary Device:									
Device Setup/Function Check ³	X	X	X		X	X	X	X	
Device Training/Re-Training ⁴	X	X	X		X	X		X	
Dispense/Collect eDiary Device	X						X		
Patient Voiding Diary:									
Patient Voiding Diary Training/Re-Training ⁵	X	X	X		X	X		X	
Patient Completes Patient Voiding Diary ⁶	X	X		X	X	X	X		
Urine Volume Diary:									
Urine Volume Diary Training/Re-Training ⁵	X	X	X		X	X		X	
Dispense Urine Collection/Measurement Supplies	X								
Patient Completes Urine Volume Diary ⁷	X	X		X	X	X	X		
Diary and Visit Reminders									
Phone Calls / Optional SMS reminders ⁸	X	X		X	X	X	X		

Study Period:	Screening/ Washout	Run-in	Treatment					Safety Follow-up/ Unscheduled	
Visit Number:	Visit #1	Visit #2	Visit #3	Diary Only	Visit #4	Visit #5	Visit #6	UNS #	Visit #7
Visit Name:	Screening ¹	Run-in	Baseline	Week 2	Week 4	Week 8	Week 12 or Early WD	Unsch- eduled ²⁵	Follow- up ²⁶
Study Day:	-49 to -15	-14	1	15	29	57	85 or Early WD		113 or Early WD + 28
Permitted Visit Window:		± 3 Days			± 3 Days	± 3 Days	± 3 Days		± 3 Days
Patient Reported Outcomes ⁹ :									
Global Impression Items (PGI-Severity, PGI-Control, PGI-Frequency, PGI-Leakage, and PGI-Change)			X		X	X	X		
Overactive Bladder Questionnaire (OAB-q LF)			X				X		
Work Productivity and Activity Impairment Questionnaire-Urinary Symptoms (WPAI-US)			X				X		
EQ-5D			X				X		
Post-Void Residual (PVR) Volume ¹⁰		X					X		
Physical Exam ¹¹	X	X						X	X
ECG ¹²	X							X	
Vital Signs ¹³	X	X	X		X	X	X	X	X
Adverse Events ¹⁴	←=====→								
Serious Adverse Events ¹⁵	←=====→								

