6.4. Missing Data

For the primary analysis of the co-primary endpoints and for all CFB analyses, no imputation of missing data will be performed as the MMRM model accounts for this.

A sensitivity analysis of the co-primary endpoints will be performed using multiple imputation (MI) for missing data and is detailed in [Section 8.1.1.2](#), as well as last observation carried forward (LOCF). For all responder analyses, multiple imputation will be used to impute missing data.

Incomplete/missing start and stop dates will be handled as follows:

Incomplete AE/Concomitant Medication Start Date

If only the start day is missing, then the start day will be imputed as the first day of the month that the event occurred with the following exceptions: (1) if the partial date is the same month and year as the date of first dose of run-in single-blind medication (or double-blind medication), then the partial date will be imputed as the date of first dose of single-blind medication (or double-blind medication). However, if the date of first dose of single-blind medication and date of first dose of double-blind medication occur in the same month, then the date of first dose of double-blind medication will be imputed. (2) if the partial date is before the date of first dose of run-in single-blind medication, then the start date will be sent as the date of informed consent.

If the start date is missing both the day and month, then the day and month will be imputed as the first day of the year (i.e., 01-Jan) with the following exceptions: if the partial date is in the same year as the first dose dose of run-in single-blind medication (or double-blind medication), then the partial date will be imputed as the date of first dose of single-blind medication (or double-blind medication). However, if the date of first dose of single-blind medication and date of first dose of double-blind medication occur in the same month, then the date of first dose of double-blind medication will be imputed. (2) if the start year is before the year of first dose of run-in single-blind medication, then the start date will be sent as the date of informed consent.

Incomplete AE/Concomitant Medication or Treatment End Date

If only the end day is missing, then the end day will be imputed as the last day (28/29/30/31) of the month of occurrence. If the patient died in the same month, then set the imputed date as the death date.

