6.5. Visit Windows

Visit windows will be assigned based on the analysis need and the type of data. There are two types of data to be assigned an analysis visit: diary data and non-diary data.

Visit Windowing for Diary Data:

For diary data (micturitions, UUI, urgency episodes, total incontinence etc.), where the assessment has been performed at a specific visit (for example confirmation of completion of diary) the assessment will be analyzed at the scheduled visit entered. For diary data whereby only a date/time is given, the record will be assigned based on the dates of the scheduled visits performed. For example, if Run-in visit occurs on 01SEP2018 and Baseline visit occurs on 14SEP2018, any diary data occurring after 01SEP2018 up to and including the day before Baseline visit (13SEP2018) will be windowed for the analysis as “Baseline”. This applies for all analysis visits except for Week 2 and Week 4 as there is no Week 2 scheduled visit; in this instance, Week 2 and Week 4 will be assigned based on the assessment being windowed as Week 4 per the above rule, and then the following windowing based on analysis day (relative to first date of double-blind medication) will be applied:

- Date of diary assessment after scheduled Baseline visit from Analysis Day 6 up to and including Analysis Day 22: Assigned as Week 2;
- Date of diary assessment on or after Analysis Day 23 up to and including the day before the scheduled Week 4 visit: Assigned as Week 4.

For diary data, with the exception of week 12 only the latest 10 complete diary day observations leading up to any scheduled visit will be included in the analysis of the diary. For week 12, the diary within the latest 10 complete diary day observation will be included if available. If not then the complete diary day observation within the latest 14 days will be included. For both scenarios, there must be 4 or more complete diary days available for the period to be analyzed. Otherwise, if there are less than 4 complete diary days available, the period will be set to missing for the analysis.

Visit Windowing for Non-Diary Data:

For any non-diary data involving two scheduled visits (OAB-q-LF, WPAI-US, EQ-5D, Physical Exam and ECG), the analysis visit will be assigned as the scheduled visit performed in the eCRF. For all other non-diary data, analysis visit will be windowed using the rules given in [Table 6.5.1](#) below. These adjusted analysis-defined windows will be

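### The Week 12/Early Termination diary has no study-day limit, so an early withdrawal diary can enter the primary analysis as Week 12

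*SAP*

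**What the plan says.** - **One visit for two purposes.** The schedule in section 3.11 has a single column, "Week 12 or Early WD". Footnote 26 has the applicable Week 12 activities done at withdrawal.
- **Diary limit.** Section 6.3 treats the Week 12/Early Termination diary as one diary: "For the Week 12/Early Termination diary, only complete diary days within 14 days prior to the study visit will be included". Sections 6.3 and 6.5 also require at least 4 complete diary days. Both conditions move with the visit; neither refers to the study day.
- **Assignment to a visit.** Under section 6.5, where a diary assessment was made at a specific visit, "the assessment will be analyzed at the scheduled visit entered". Where there is only a date, "the record will be assigned based on the dates of the scheduled visits performed". The section adds: "This applies for all analysis visits except for Week 2 and Week 4 as there is no Week 2 scheduled visit". Records first placed at Week 4 are then split by analysis day: Days 6-22 become Week 2, and Day 23 to the day before the Week 4 visit becomes Week 4.
- **Table 6.5.1.** Its Week 12 window, Days 71-98, is introduced for non-diary data.
- **Missing data.** Section 6.4 imputes nothing for change-from-baseline analyses because the MMRM deals with missing values, and names LOCF only as a sensitivity analysis. "For all responder analyses, multiple imputation will be used to impute missing data".
- **Sample size.** Section 3.8 assumes 10% discontinue before Week 12, leaving about 450 evaluable per main arm, and about 337 for incontinence.

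**The concern.** The primary inference is the vibegron-placebo difference at Week 12. Suppose a patient attends Week 4, completes the diary on Days 50-56 and has a withdrawal visit on Day 57. If that visit is recorded as the combined Week 12/withdrawal visit, nothing readable keeps the diary out of Week 12. A Week 8 value then stands in for Week 12, much as LOCF would, inside the model meant to handle that missing value under MAR. In the responder analyses it displaces multiple imputation.

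The same visit would also be split: the PGI items from Day 57 go to Week 8 under Table 6.5.1, the diary to Week 12. And two competent programmers could build different Week 12 data sets for both co-primary endpoints from this text. The direction of any bias depends on when, and in which arm, patients leave.

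**Working it through.** **1. The plan's own power (section 3.8).** SE = SD × √(2/n); power = Φ(difference/SE − 1.96).
- Micturitions: 2.20 × √(2/450) = 0.147; 0.6/0.147 = 4.09; power 98.3% (stated 98%).
- UUI: 1.68 × √(2/337) = 0.129; 0.51/0.129 = 3.94; power 97.6% (stated 98%).
- Joint, uncorrelated: 0.983 × 0.976 = 0.960 (stated 96%).

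**2. Withdrawal days that give a usable diary.** Footnote 6 of the schedule puts diary days at 8-14, 22-28, 50-56 and 78-84. For each withdrawal day D from 2 to 84 (83 days), count diary days from D−14 to D−1 since the last visit performed; the diary is usable with 4 or more.
- Earlier visits kept (Days 29 and 57): D = 12-29 and 54-57, so 18 + 4 = 22 days.
- Last due visit missed: D = 12-39 and 54-67, so 28 + 14 = 42 days.
- D = 82-84 is also usable but lies inside Days 71-98, so it is no problem.

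The Day 6-22 rule works on records already placed at Week 4, so it may not reach a patient with no Week 4 visit. If it does reach them, the days become 27-29 and 54-57 (3 + 4 = 7), or 27-39 and 54-67 (13 + 14 = 27).

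**3. Patients affected.** 10% of 500 is 50 withdrawers per main arm; 10% of 375 OAB Wet is 37.5. Assumptions: withdrawal visits are spread evenly over Days 2-84, and every withdrawer attends one with all scheduled diary days complete.

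| Case | Share of days | Per main arm | OAB Wet |
|---|---|---|---|
| Visits kept, Week 2 rule reaches | 7/83 | 4 | 3 |
| Visits kept, it does not | 22/83 | 13 | 10 |
| Last visit missed, rule reaches | 27/83 | 16 | 12 |
| Last visit missed, it does not | 42/83 | 25 | 19 |

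**4. Shift in the Week 12 micturition difference.** Assumed, not SAP figures: placebo change −0.7/−1.0/−1.2/−1.3 and effect −0.30/−0.45/−0.55/−0.60 at Weeks 2/4/8/12, placed at the middle of each diary week (Days 11, 25, 53, 81) and interpolated. In each arm the weight of early diaries is w = f·p/(1 − p + f·p), where p is dropout and f the share of days in step 3. The arm mean is (1 − w) × Week 12 mean + w × mean of the early diaries.

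Equal 10% dropout:
- f = 22/83: w = 0.0265/0.9265 = 0.0286; mean early effect −0.362; −0.60 + 0.0286 × 0.238 = −0.593, or 0.05 SE.
- f = 42/83: w = 0.0506/0.9506 = 0.0532; mean early effect −0.427; −0.60 + 0.0532 × 0.173 = −0.591, or 0.06 SE.

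Dropout 5% placebo, 15% vibegron:
- f = 22/83: weights 0.0138 and 0.0447; mean early placebo change −0.819. Placebo: −1.3 + 0.0138 × 0.481 = −1.2934. Vibegron: −1.9 + 0.0447 × 0.719 = −1.8679. The difference is −0.574, or 0.17 SE.
- f = 42/83: the same steps with −0.951 and −0.427 give −0.566, or 0.23 SE.
- With the imbalance reversed, the difference is −0.612 to −0.615, away from zero.

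These shifts belong to the higher counts. At the lower counts they shrink. For f = 27/83 at equal dropout, w = 0.0325/0.9325 = 0.0349, mean early effect −0.500, and −0.60 + 0.0349 × 0.100 = −0.597, or about 0.02 SE.

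UUI, taking the same placebo course and a proportional effect, gives −0.504 to −0.502 at equal dropout and −0.486 to −0.478 at 5%/15%, against −0.51. The lowest power in these cases is 97.1% for micturitions and 95.9% for UUI.

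**5. Extreme case.** If every withdrawal fell on Day 29 with a usable diary, w = p. Equal dropout gives −0.60 + 0.10 × 0.15 = −0.585 (0.10 SE). At 5%/15% it is −1.8325 + 1.285 = −0.548 (0.36 SE), with power 96.2%.

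**The case against.** - **No sentence says that a withdrawal diary becomes Week 12.** This stands, so the point is that it can enter, not that it must. A Day 57 visit could be entered as Week 8. Days 27-29 and 54-57 also lie within 3 days of the Week 4 and Week 8 targets. That only shows that the outcome turns on how a site labels the visit.
- **The Day 6-22 rule may already hold early entries in Week 2.** This is arguable and lowers the counts to 4 and 16 per arm. It leaves the later diaries untouched.
- **The counts assume that every withdrawer attends with a full diary.** Correct. The 10% covers discontinuation for any reason, and section 6.3 recognises loss to follow-up. They are upper figures.
- **Per-protocol analyses may exclude missed or out-of-window visits.** They are supportive only and do not settle the rule for the FAS and FAS-I.
- **OAB-q LF is also assigned by the eCRF visit.** True, but it has one post-baseline assessment and no earlier slot, so the comparison is loose.
- **Section 8.1.1.2, the list in section 10 and Appendix 1 are not visible.** A rule there cannot be excluded. Sections 6.3 and 6.5, which govern diary windowing, can be read and contain none.

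A reader might infer that the plan makes LOCF its primary method, that all 50 withdrawers per arm are affected, or that the co-primary result is at risk. The documents support none of these. Most withdrawal days give no usable out-of-window diary in three of the four cases in the table, and about half do in the fourth. Power stays high throughout.

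**Conclusion.** The gap is real and of minor to moderate weight. As readable, the plan lets an LOCF-like value into the primary Week 12 analysis and the responder analyses, against the handling of missing data in section 6.4. At most about 4-13 patients per main arm are affected if earlier visits were kept and 16-25 if the last due visit was missed; the absolute ceiling is 50. At the higher counts the micturition shift is 0.05-0.06 SE with equal 10% dropout, toward zero, and 0.17-0.23 SE at 5%/15%. The timing of withdrawals, full diaries, trajectories and unequal dropout are all assumptions. The main harm is to the meaning and reproducibility of the Week 12 estimate, with a modest bias if dropout differs by arm.

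**What to change.** Before unblinding, state in sections 6.3 and 6.5:
1. An early-termination diary is analysed as Week 12 only if the withdrawal visit falls in Days 71-98.
2. Otherwise each complete diary day is assigned by analysis day, whether or not a Week 4 or Week 8 visit took place: Days 6-22 to Week 2, Days 23-42 to Week 4, Days 43-70 to Week 8.
3. The 4-complete-day minimum applies to each visit, no diary day is used twice, and a visit value already derived is not replaced.
4. Week 12 stays missing for the MMRM and multiple imputation. Such values are carried to Week 12 only in the LOCF sensitivity analysis.

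Assignment should be day by day, because a diary can straddle the split. A withdrawal on Day 24 looks back on Days 10-14, 22 and 23, and six of those seven days fall in the Week 2 range.

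The cost is wording and one derivation rule. A few Week 12 values become missing; planned power is unchanged because it already assumes 450 and 337 evaluable. FAS membership should rarely change, since under section 6.3 "the patient must have both a baseline diary and a post-baseline diary from any post-baseline timepoint, after analysis window has been applied". The exception is a patient whose only complete days straddle the split: Days 22-25 alone give one day in Week 2 and three in Week 4, so neither visit reaches the minimum. Such patients should be listed.
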